#### **11.1.2.3.6. Cancers**

The development of a new primary cancer should be regarded as an AE and will generally meet at least one of the serious criteria (see [Section 11.1.2.1.3](#)). New primary cancers are those that are not the primary reason for the administration of the study treatment and have developed after the inclusion of the patient into the study. They do not include metastases of the original cancer. Symptoms of metastasis or the metastasis of the disease under study should not be reported as an AE/SAE, as they are considered to be disease progression.

#### **11.1.2.3.7. COVID-19**

Because much is still unknown about how SARS-CoV-2 affects the human body, patients who have tested positive for COVID-19 will be identified and relevant information collected. All patients should provide documentation of any testing for COVID-19, if available, along with the test results, at screening for enrollment and/or during the study. Prior test results should be reported, if available, for any patient who has previously tested positive for COVID-19

SARS-CoV-2 titers (antiviral immunoglobulin G [IgG] and immunoglobulin M [IgM]). These data will be entered into the patient’s study-specific record.

Any patient-reported illness of COVID-19 during the study should be recorded as an AE. If a patient reports infection with COVID-19, the investigator may discuss with the Medical Monitor whether the patient can continue on study.

**11.1.2.3.8. Deaths**

All events leading to the clinical outcome of death occurring during the SAE reporting period (from the signing of the informed consent through 30 days after the last investigational agent administration) are to be reported to Sponsor or designee as an SAE and recorded on the AE eCRF.

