## 6.6. Safety Review Committee

The Safety Review Committee (SRC) for Phase 1b dose-escalation will be chaired by the [REDACTED]. The SRC will include the Principal Investigator (or delegate) from each of the investigational sites. The SRC will also include a representative from [REDACTED] PV (or designee), an [REDACTED] Biostatistician (or designee), and a representative from [REDACTED] Clinical Research. The SRC will review the safety and tolerability of DSP-7888 Dosing Emulsion in combination with nivolumab and pembrolizumab in each cohort to decide the next dose level to be tested. In addition, all immune-related AEs occurring in Arm 1 and Arm 2 will be evaluated throughout the conduct of this study. The SRC's review and assessment will include all available safety data from each cohort, together with available PD data. The SRC's review will also include an assessment of all cases, individually and in aggregate, for those patients who meet the criteria for DLT in order to determine the clinical significance and basis for their inclusion or exclusion in the decision for dose change.

The SRC will review and agree on the recommended maximum tolerated dose prior to enrolling patients in the dose-expansion part. In the dose-search cohort (Phase 1b), the stopping rule will follow the rule of the 3+3 design. All decisions made by the SRC will be documented and provided in writing to the investigators before dosing any new patients.

In Phase 2 of the study, the Sponsor will decide the necessity for a study suspension, protocol amendment, continuation of enrollment, or termination of the study if the following criteria are met:

- Any cases of death (other than death related to progressive disease) that occur from the start of treatment with DSP-7888 Dosing Emulsion and up to 30 days from the last DSP-7888 Dosing Emulsion administration, and deemed by the Sponsor to be related to any of the study's drugs
- If the percentage of patients in this study presenting with drug-related (assessed by Sponsor) Grade 4 or higher AE within a particular medical concept (eg, hypersensitivity) is higher than that reported in patients treated with DSP-7888 Dosing Emulsion within the clinical program, and as reported in the literature

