#### **11.1.2.1.3. Serious Adverse Event**

An SAE is any adverse experience occurring at any dose that results in any of the following outcomes:

- Death
- Life-threatening experience
  - Note: “Life-threatening” refers to a situation in which the patient was at risk of death at the time of the event as it occurred; it does not refer to an event that might have caused death if it were more severe;
- Requires inpatient hospitalization or prolongation of existing hospitalization, unless the hospitalization is for the following:
  - Elective or pre-planned treatment for a pre-existing condition that is unrelated to the indication under study and has not worsened since signing the ICF (as documented as medical history on the eCRF).
  - Scheduled therapy for the target disease of the study, including admissions for transfusion support or convenience
- Results in congenital anomaly or birth defect
- Results in persistent or significant disability or incapacity
- Is considered to be an important medical event.

Note: Important medical events are those that may not be immediately life-threatening or result in death or hospitalization but may jeopardize the patient or may require intervention to prevent one of the outcomes listed in the definition above. Examples of such medical events include allergic bronchospasm requiring intensive treatment in an emergency room or at home, blood dyscrasias or convulsions that do not result in inpatient hospitalization, or the development of drug dependency or drug abuse.

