#### 11.1.2.2.3. Adverse Event Severity

The severity of AEs will be assessed according to the National Cancer Institute (NCI) Common Terminology Criteria for Adverse Events (CTCAE), v4.03. For events not specifically found in CTCAE, the following definitions will be used to estimate grade of severity:

- Grade 1: Mild; asymptomatic or mild symptoms; clinical or diagnostic observations only; intervention not indicated
- Grade 2: Moderate; minimal, local or noninvasive intervention indicated; limiting age appropriate instrumental activities of daily living (ADL)
- Grade 3: Severe or medically significant but not immediately life-threatening; hospitalization or prolongation of hospitalization indicated; disabling; limiting self-care ADL
- Grade 4: Life-threatening consequences; urgent intervention indicated
- Grade 5: Death related to AE

The term "severe" is often used to describe the intensity (severity) of a specific event (as in mild, moderate, or severe myocardial infarction); the event itself, however, may be of relatively minor medical significance (such as severe nausea). This is not the same as "serious," (outlined in [Section 11.1.2.1.3](#) which is based on patient/event outcome or action criteria usually associated with events that pose a threat to a patient's life or functioning.

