5.4.1. Adverse Events

Treatment-Emergent Adverse Events

An AE will be regarded as treatment-emergent, if

- it occurs for the first time on or after the first dose date of either DSP-7888 or CPI up to 30 days after the last dose of study drug; or
- it occurs up to any time if serious and considered related to study drug.

The emphasis for AE analysis will be based on treatment-emergent AE (TEAE), however all AEs will be listed.

All AEs will be coded using Medical Dictionary for Regulatory Activities (MedDRA version 20.0) and summarized by MedDRA System Organ Class and Preferred Term. The severity of all AEs will be graded by the Investigator using NCI CTCAE version 4.0.

An overview of treatment-emergent adverse events (TEAEs) will be provided. The number and percentage of subjects with following will be summarized for phase 1b, Arm 1 and Arm2 overall, phase 2: CPS < 10, CPS \geq 10 and Overall.

- Subjects with any TEAE
- Subjects with TEAE of CTCAE grade 3 or higher
- Subjects with serious adverse events (all causality and related)
- TEAEs related to study drug
- TEAEs related to study drug with CTCAE grade 3 or higher
- Subjects with TEAE leading to study drug discontinuation (all causality and related)
- Subjects with TEAE leading to study drug dose reduction (all causality and related)
- Subjects with TEAE leading to study drug dose interruption (all causality and related)

Summary of AEs by SOC and Preferred Term

The number and percentage of subjects with TEAEs by SOC, PT and maximum CTCAE grade will be summarized. A summary of TEAEs of CTCAE grade 3 or higher (Grade 3, 4, 5) will be presented by SOC and PT and maximum CTCAE grade (All Grade, \geq Grade 3).

The number and percentage of patients who experience any TEAE will be summarized by SOC and PT (All Grade, \geq Grade 3). A summary of TEAEs by PT and maximum CTCAE grade will be presented. The most commonly reported TEAEs using a different cutoff (e.g. 2% or 10% or more of patients in either arm) may also be summarized by PT as needed.

TEAEs associated with permanent discontinuation /dose reduction/drug interruption of either DSP7888 and/or CPI will be summarized by SOC and PT and maximum CTCAE Grade (taking into consideration the action taken from CRF AE page).

Treatment Related Adverse Events

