Treatment-related TEAEs are those judged by the investigator to be at least possibly related to the study drugs (DSP7888 and/or CPI) or for which relatedness is recorded as “unknown” by the investigator. Treatment related will include “possible”, “probable” or “definite” causality assessments. Missing relationship will be considered as “Related” to all drugs received by the patient. Similar summaries as noted for all causality TEAEs will be provided for treatment related TEAEs.

Serious Adverse Events and Death

Treatment-emergent SAEs and Treatment-related SAEs will be summarized by MedDRA SOC and PT and maximum CTCAE grade.

TEAE leading to death will be summarized by MedDRA SOC and Preferred Term.

Deaths will be summarized by on study and on treatment (within 30 days of last dose of study medication). The number and percentage of patients who died on study and on treatment, as well as primary cause of death will be summarized. Deaths may also be categorized according to time of occurrence after first dose.

A listing of death data will also be provided and will include all deaths that occurred from the signing of the informed consent to the end of the follow up period. The listing will include primary cause of death and the number of days relative to the administration of first and last dose.

Adverse Events of COVID-19

Preferred Terms corona virus infection and coronavirus test positive will be used to identified COVID-19 positive cases in adverse event.

Injection Site Reaction (ISR)

The predominant adverse effect observed with DSP-7888 is injection site reaction. The Preferred Terms of TEAEs within the High Level Group Term of “Administration Site Reaction” (MedDRA version 20.0) will be used to identify events of injection site reaction.

Below analysis will be provided for ISR:

- ISR by SOC, PT, and maximum CTCAE Grade
- Onset time of first ISR for patients with at least one ISR: Time to onset is analyzed for patients with at least one ISR from the first dose of the DSP-7888 to the first occurrence of ISR regardless of CTCAE grade.
- Onset time of first ISR: Time to first ISR is defined as the time from the first dose of the DSP-7888 to the first occurrence of ISR . For patients with no ISR, the onset time will be censored as data cutoff date,

end of study date, death date, or safety follow-up completion date (end of treatment date + 30 days) whichever is shorter.

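### A death from metastatic progression may be recorded as a fatal SAE or left off the AE form, both in compliance with the protocol, and the SAP's AE tables have no step for it

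*Protocol*

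**What the plan says.** Two protocol sections bear on the same patient.

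- **Protocol 11.1.2.3.6 (Cancers)** separates new primary cancers, which are AEs, from metastases of the study cancer. Of the latter and their symptoms it says that they "should not be reported as an AE/SAE, as they are considered to be disease progression". It makes no exception for a fatal outcome.
- **Protocol 11.1.2.3.8 (Deaths)** covers "All events leading to the clinical outcome of death occurring during the SAE reporting period", from consent to 30 days after the last dose. These events "are to be reported to Sponsor or designee as an SAE and recorded on the AE eCRF". It makes no exception for progression.

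SAP 5.4.1 defines a TEAE as an AE that starts on or after the first dose, "up to 30 days after the last dose of study drug" (longer if serious and related). From the recorded AEs it then builds an overview, tables of Grade 3 to 5 events, SAE tables and a fatal-event table: "TEAE leading to death will be summarized by MedDRA SOC and Preferred Term". It counts an AE with missing or unknown relationship as treatment-related. It says nothing about terms for progression of the study disease.

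SAP 5.4.1 also plans something that does not depend on AE recording: a summary of deaths on study and on treatment with primary cause, and a listing of every death with its cause and its timing from first and last dose.

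**The concern.** The final report is a synoptic, safety-focused one (SAP 5, 5.5), so the AE tables are its main content. Phase 2 is single-arm, so no control rate shows how much of a fatal-event percentage reflects the underlying disease.

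The situation is a plausible one in this population. Clinically stable patients continue study treatment after RECIST progression until progression is confirmed under iRECIST (Protocol 6.1.4.4), so dosing can run into progressive disease. Protocol 4.1 gives a PFS of 3 to 4 months and a median survival under a year after platinum resistance.

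If a death from metastatic progression falls within 30 days of the last dose, the AE-based fatal-event rate depends on which section was followed when the form was completed. With 20 to 40 patients, one or two such choices are visible in the headline percentage, and a reader of that percentage cannot tell which choice was made.

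**Working it through.** The plan states no figure to reproduce here. The check compares the texts, follows them into the tables, and works out what one patient is worth.

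**1. Does any other text decide which section governs?**

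| Place | What it contributes | Does it settle the matter? |
|---|---|---|
| Protocol 11.1.2.1.3 | "An SAE is any adverse experience occurring at any dose that results in any of the following outcomes"; death is listed first and progression is not excluded | No. It presupposes an adverse experience, and 11.1.2.3.6 withholds that status from metastasis and its symptoms |
| Protocol 11.1.2.2.3 | "Grade 5: Death related to AE" | No. The grade exists only if an AE is recorded |
| Protocol 6.6 | "Any cases of death (other than death related to progressive disease" and so on | No. This is a Phase 2 criterion for considering suspension, not a recording rule |
| SAP 5.4.1 | Counts recorded AEs | No. It takes the recording as given |

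Neither 11.1.2.3.6 nor 11.1.2.3.8 refers to the other.

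**2. Where does the choice appear?** Take one treated Phase 2 patient who dies of metastatic progression within 30 days of the last dose, with no other AE recorded as the cause of death.

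| Output | Recorded (11.1.2.3.8) | Not recorded (11.1.2.3.6) |
|---|---|---|
| TEAE leading to death | one patient more | unchanged |
| Any SAE | one more, only if the patient has no other SAE | unchanged |
| Grade 3 or higher | one more, only if the patient has no other such TEAE | unchanged |
| Treatment-related versions | as above, if causality is blank, unknown or at least possible | unchanged |
| Deaths by primary cause; death listing | counted | counted |

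**3. How much is one patient worth?** The change is 1/n. SAP 2.3 gives Phase 2 as about 20 to 40 patients, with a cap of 60.

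- n = 20: 1/20 = 5.0 percentage points
- n = 40: 1/40 = 2.5 percentage points
- n = 60: 1/60 = 1.7 percentage points

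**4. What is the total shift?** With d such deaths it lies between 0 and d/n for the fatal-TEAE rate. The documents do not give d, so the total cannot be computed.

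**The case against.** The strongest reply is that the two sections can be read together. Section 11.1.2.3.6 sits under a heading on cancers, its purpose is to separate new primaries from metastases, and it does not mention death. Section 11.1.2.3.8 is the specific rule for fatal outcomes. On that reading non-fatal metastatic events are not AEs, while any event that leads to death in the window is always an SAE. The reading is coherent. It would settle the matter if the protocol stated it, but no sentence does, and the reason given in 11.1.2.3.6 applies equally to a fatal case.

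Other points on this side carry weight:

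- Fatal TEAEs and SAEs are shown by Preferred Term, so a recorded progression term would normally appear under its own name. This stands, but overview totals carry no terms, and an unrecorded death leaves no row to see.
- Treatment-related events are tabulated separately. This stands, apart from the rule that counts missing causality as related.
- Fatal SAEs reach the sponsor within 24 hours, inconsistent data are queried, and the SAP relies on an annotated CRF that is not among these documents. Practice may therefore be more uniform than the text.

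A reader might infer more than the documents support:

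- **That the protocol excludes all disease progression from AE reporting.** It names metastasis of the study disease and its symptoms. The wider rule is implied by its reason but not stated.
- **That sites do record these deaths differently.** The text permits it; nothing shows that it happens.
- **That progression deaths vanish from the report, or that toxicity cannot be told from disease.** The summary and listing of deaths by primary cause rule out the first and much reduce the second.

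**Conclusion.** The gap is real but narrow. Two compliant recordings of the same death from metastatic progression give different fatal-TEAE counts, and sometimes different SAE, Grade 3 or higher and treatment-related counts. Neither document says which recording applies. All-cause mortality and its causes are unaffected.

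Each such death is worth 2.5 points on the Phase 2 fatal-TEAE rate at 40 patients and 5.0 points at 20. The SAE and Grade 3 or higher rates move only if the patient has no other qualifying event. These figures assume that the recorded event meets the TEAE definition and that no other AE is recorded as the cause of the death.

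The total effect is unknown. A reader might take the protocol's survival figure to imply a rate, for instance 5% to 15% of 40 patients (0.05 × 40 = 2 to 0.15 × 40 = 6). The documents do not support that: a median survival after platinum resistance does not say how many patients die of progression within 30 days of their last dose.

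The point merits a small change, because the report rests on its safety tables and the remedy needs no new data.

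**What to change.** 1. **Protocol.** Reconcile 11.1.2.3.6 and 11.1.2.3.8 so that one recording rule applies to a death from progression of the study disease. Either direction closes the gap, and the documents do not show which was intended. Since Phase 2 has already been terminated, this cannot change what has been recorded, so the SAP step does most of the work.
2. **SAP 5.4.1, term list.** Before database lock, fix a list of Preferred Terms that denote progression of the study disease. The study is open-label, so the safeguard is that the list is fixed before the tables are run.
3. **SAP 5.4.1, display.** Show the overview, fatal-TEAE, SAE and Grade 3 or higher counts with and without those terms. This is preferable to removing the events, which would make the tables disagree with the SAE reports.
4. **SAP 5.4.1, cross-check.** Beside these, cross-tabulate on-treatment deaths by primary cause (study disease or other) against whether a fatal AE was recorded (yes or no). Recorded and unrecorded progression deaths are then both visible.

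The cost is a few table rows and a short term list. The drawback is that the counts without progression terms rely on the investigator's attribution of the event to progression, which a footnote should state.

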**11.1.2.4. Reporting of Expedited Safety Observations by the Investigator Including Serious Adverse Events**

**11.1.2.4.1. Immediate Reporting of Serious Adverse Events by Investigator to Sponsor**

All SAEs, from the signing of informed consent through 30 days after last dose, including SAEs from screen failures, will be reported to the Sponsor or designee within **24 hours** of the Investigator’s first knowledge of the event, even if the experience does not appear to be related to the investigational agent.

Serious AEs should be communicated on an SAE report form as follows:

[REDACTED] Pharmacovigilance Department Contacts	
Email:	[REDACTED]
Fax:	[REDACTED]

The initial SAE report must be as complete as possible, including details of the current illness and SAE, and an assessment of the causal relationship between the event and the investigational product(s). Information not available at the time of the initial report (eg, an end date for the AE, laboratory values received after the report, or hospital discharge summary) must be documented on a follow-up form. All follow-up information must be reported in the same timelines as initial information.

At any time after completion of the AE reporting period (ie, 30 days post-treatment), if an Investigator becomes aware of an SAE that is suspected by the Investigator to be related to the investigational agent, the event must be reported to the Sponsor or designee.

**11.1.2.4.2. Immediate Reporting of Occupational Exposure, Overdose, or New Cancers**

Any **occupational exposure** or exposure of an individual not enrolled in the study to the investigational medicinal product must be reported to the Sponsor or designee within **24 hours** of the Investigator’s first knowledge of the event, even if the exposure does not result in an AE. Unintentional exposures should be communicated on the SAE Report Form, as described above for SAEs.

Any **overdose** to the investigational medicinal product must be reported to the Sponsor or designee within **24 hours** of the Investigator's first knowledge of the event, even if the overdose does not result in an AE. Overdose should be communicated on the SAE Report Form, as described above for SAEs.

Any **new cancers** must be reported to Sponsor or designee within **24 hours** of the Investigator's first knowledge of the event. New cancers should be communicated on the SAE Report Form, as described above for SAEs.

#### **11.1.2.4.3. Reporting COVID-19 Infections**

Suspected or confirmed COVID-19 infections, including asymptomatic infections and positive COVID-19 tests are Adverse Events of Special Interest (AESIs) and therefore immediately reportable events, even if the events do not meet SAE criteria.

Serious COVID-19 events will be reported on an SAE Report form within 24 hours of the investigator's awareness, according to [Section 11.1.2.4.1](#).

Nonserious COVID-19 events will be reported on a COVID-19 Report form within 5 calendar days of the investigator's awareness, to the same email/fax for reporting SAEs described in [Section 11.1.2.4.1](#).

Updates or follow-up information for COVID-19 events should be reported on an SAE Report form (serious events) or a COVID-19 Report form (nonserious events) within the same timelines as the initial reports.

#### **11.1.2.4.4. Reporting Pregnancies**

If a female patient or the female partner of a male patient becomes pregnant during the course of study, the Investigator must report the pregnancy to the Sponsor or designee using the **Pregnancy Reporting Form** within **24 hours** of becoming aware of the event.

If not all information on the Pregnancy Reporting Form is available at the time of the initial report, follow-up Pregnancy reports will be completed and submitted within **24 hours** of becoming aware of the new information. The Investigator is required to follow up on the pregnancy until it has completed. The outcome of the pregnancy and the status of the newborn (if applicable) will be reported on the Pregnancy Reporting Form within **24 hours** of becoming aware. SAEs associated with the pregnancy, including fetal death, miscarriage or congenital anomalies, must be reported as a serious adverse event according to [Section 11.1.2.4](#).

If the female partner of a male patient becomes pregnant, the Investigator must obtain consent to collect pregnancy information from the pregnant partner (including the status of the newborn, if applicable).

